3.6.3 Additional safety assessments

3.6.3.1 Laboratory variables, vital signs and electrocardiograms (ECGs)

The following laboratory variables, vital signs and electrocardiogram (ECG) variables will be analyzed. They will be converted into standard international units.

- Hematology:
 - Red blood cells and platelets: hemoglobin, hematocrit, red blood cell count, platelet count, red blood cell indices (MCV, MCH, %Reticulocytes)
 - White blood cells: white blood cell count, neutrophils, lymphocytes, monocytes, basophils, eosinophils

- Clinical chemistry:
 - Metabolism: glucose, total protein, lipase, amylase
 - Electrolytes: sodium, potassium, calcium
 - Renal function: creatinine, creatinine clearance, eGFR, blood urea nitrogen, uric acid
 - Liver function: alanine aminotransferase, aspartate aminotransferase, alkaline phosphatase, gamma glutamyl transferase, total and direct bilirubin
 - Pregnancy test: urine human chorionic gonadotropin (hCG) (as needed for women of childbearing potential)
- Vital signs: heart rate, systolic and diastolic blood pressure in sitting position, and weight
- ECG variables: ECG assessments will be described as normal, abnormal and clinically significant (Y/N) if abnormal

Data below the lower limit of quantitation/detection limit (LLOQ) will be replaced by half of the LLOQ, data above the upper limit of quantification will be replaced by ULOQ value.

Quantitative analyses

When relevant, for laboratory variables and vital signs above, descriptive statistics for results and changes from baseline will be provided for each visit, the last value and the worst value (minimum and/or maximum value depending on the parameter) during the on-treatment period. These analyses will be performed using central measurements only (when available) for laboratory variables.

Analyses according to PCSA

Potentially clinically significant abnormality (PCSA) analyses will be performed based on the PCSA list currently in effect at Sanofi at the time of the database lock. For parameters for which no PCSA criteria are defined, similar analyses will be done using the normal range, if applicable. For parameters defined as efficacy endpoints, PCSA summaries will not be provided.

Analyses according to PCSA will be performed based on the worst value during the treatment-emergent period, using all measurements (either scheduled, nonscheduled or repeated).

For laboratory variables and vital signs above, the incidence of participants with at least one PCSA during the treatment-emergent period will be summarized regardless of the baseline level and according to the following baseline status categories:

- Normal/missing
- Abnormal according to PCSA criterion or criteria

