| HbA1C | X | | | | | X | | X | | X | | X | | X | X | |

| Study period | Screening | Randomization | Study treatment period | | | | | | | | | | | | | Follow-up |
|---|-----------|----------------|------------------------|------|---|------|---|------|----|------|----|------|----|----------------|------------------|-------------|
| Visit number | 1 | 2 ^a | 3 | 4 | 5 | 6 | 7 | 8 | 9 | 10 | 11 | 12 | 13 | 14 | E/D ^d | 15 |
| Visit type (on-site/phone) ^b | site | site | ☎ | site | ☎ | site | ☎ | site | ☎ | site | ☎ | site | ☎ | site | site | ☎ |
| Week ^b | -2 | 0 (Day 1) | 1 | 2 | 3 | 4 | 6 | 8 | 10 | 12 | 15 | 18 | 21 | 24 | E/D | 24 + 3 days |
| FPG ^m | X | X | | | | X | | X | | X | | X | | X | X | |
| Fasting C-peptide ^m | | X | | | | | | | | | | | | X ⁿ | X | |
| Safety laboratory ^k hematology, serum chemistry | X | | | | | X | | X | | X | | X | | X | X | |
| Amylase, lipase, calcitonin | X | | | | | X | | X | | X | | X | | X | X | |
| FSH, estradiol (if necessary to confirm menopausal status) | X | | | | | | | | | | | | | | | |
| Urine pregnancy test ^l (women childbearing potential only) | X | X | | X | | X | | X | | X | | X | | | | |

- a Randomization (V2) can be performed less than 2 weeks after screening visit (V1) if the laboratory data are available.
- b Additional phone calls between visits for titration purposes should be scheduled as often as deemed necessary by the Investigator
- c Visit widows listed in the table are acceptable always using Day 1 (V2) as reference. A visit window of -1 day or +3 days for the post-treatment follow-up visit (V15) is acceptable using the day of V14 as reference. If one visit date is changed, the next visit should take place according to the original schedule.
- d **E/D= Early IMP discontinuation**, participants should have an onsite visit as soon as possible with the assessments (except 7-point SMPG) normally planned at the end of treatment visit (V14). Afterward, the patients should continue in the study up to the scheduled date of study completion. They should be followed up according to the study procedures as specified in the protocol. **In case of rescue therapy**, all assessments (except 7-point SMPG) planned at V14 should be performed before starting rescue therapy, participants then continue the study treatment (including background therapy if appropriate), and all visits and assessments should be performed as scheduled.
- e Systolic and diastolic blood pressure, heart rate.

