2.3 BENEFIT/RISK ASSESSMENT

2.3.1 Risk assessment

Table 1 - Risk assessment

| Potential risk of clinical significance | Summary of data/rationale for risk | Mitigation strategy |
|---|--|--|
| 
Study intervention: Hypersensitivity to any of its ingredient Hypoglycemia caused by the study interventions Overdose due to medication errors Injection site reactions GI AEs, including nausea, diarrhea, and vomiting caused by iGlarLixi (lixisenatide) Acute pancreatitis Thyroid medullary cell cancer
 | 
For details about data and rationale of the risks, please refer to the current version of Investigator's Brochure, Section 7.
 | 
Participants with known allergy to GLP-1 RA or insulin products will be excluded. Investigator will educate the participants to seek immediate medical attention if suspected event with symptoms and signs.
 
Participants will be monitored for hypoglycaemia through SMPG and to be educated how to treat hypoglycemia at home or seek to medical attention as needed.
 
Participants will be well trained in self-injection before the 1st dosing and at the time when a participant needs to shift injection pen from 1:1 to 2:1 pen (iGlarLixi). In addition, there will be more training opportunities in case any injection issue is observed at the onsite visits. The occurrence of dosing error could be efficiently minimized.
 
Participants will be educated to change injection location (abdominal wall, thighs or upper arms) at each time of injection to avoid the injection site skin reaction.
 
The GLP-1 class effect of GI reactions will be reduced with low starting dose (5 µg/lixisenatide). With the titration procedure ie, dose increase every week, the participants may tolerate better to higher doses (up to 20 µg).
 
Patients with amylase and/or lipase >3 times the upper limit of normal (ULN) will be excluded from participation in this study. Pancreatic enzymes will be monitored during the study. Participants are instructed to seek medical attention and report any symptoms of abdominal pain to the investigator.
 
C-cell hormone calcitonin is measured at screening and patients with calcitonin ≥20 pg/mL (5.9 pmol/L) will be excluded from participation in the study.
 |
| 
Study procedures: Not applicable
 | | |
| 
Other: Not applicable
 | | |

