9.3.5.3 Laboratory variables, vital signs and electrocardiograms (ECGs)

Quantitative analyses

For laboratory variables, vital signs and ECG variables, descriptive statistics for results and changes from baseline will be provided for each planned visit during the on-treatment period. The central laboratory measurements for safety parameters will be analyzed.

Analyses according to PCSA

The number (n) and percentage (%) of participants with PCSA at any evaluation during the on-treatment period will be summarized for each parameter within each treatment group. The summaries will include participants in the safety population who have at least one parameter to be analyzed during the on-treatment period. When the PCSA definition involves the change from the baseline value, participants need also to have a baseline value to be included in the summaries.

Tabular and graphical methods may be used to present the results for parameters of interest.

Listings will be provided with flags indicating the PCSA values.

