10.2 APPENDIX 2: CLINICAL LABORATORY TESTS

- The tests detailed in below [Table 8](#) will be performed by the central laboratory.
- Local laboratory results are only required in the event that the central laboratory results are not available in time for either study intervention administration and/or response evaluation. If a local sample is required, it is important that the sample for central analysis is obtained at the same time. Additionally, if the local laboratory results are used to make either a study intervention decision or response evaluation, the results must be recorded.
- Protocol-specific requirements for inclusion or exclusion of participants are detailed in [Section 10.5](#) of the protocol.
- Additional tests may be performed at any time during the study as determined necessary by the Investigator or required by local regulations [(for instance, when participants with known acquired immunodeficiency syndrome (AIDS)-related illness or known HIV disease requiring antiviral treatments need to be excluded, an HIV serology testing at screening is mandatory for German participants)].

Table 8 - Protocol-required laboratory tests

| Laboratory tests | Parameters |
|---------------------------------|--|
| Hematology | Platelet count Red blood cell (RBC) count Hemoglobin Hematocrit RBC indices: 
 • MCV • MCH • %Reticulocytes White blood cell (WBC) count with differential: 
 • Neutrophils • Lymphocytes • Monocytes • Eosinophils • Basophils |
| Clinical chemistry ^a | Blood urea nitrogen (BUN) Creatinine Glucose [Indicate if fasting, or nonfasting] Potassium Sodium Calcium Aspartate aminotransferase (AST)/ Serum glutamic-oxaloacetic transaminase (SGOT) Alanine aminotransferase (ALT)/ Serum glutamic-pyruvic transaminase (SGPT) Alkaline phosphatase ^b Total and direct bilirubin Total protein Amylase Lipase Calcitonin |
| Pregnancy testing | 
 • Urine human chorionic gonadotropin (hCG) pregnancy test (as needed for women of childbearing potential)^c |
| Other screening tests | 
 • Follicle-stimulating hormone and estradiol (as needed in women of non-childbearing potential only) • All study-required laboratory tests will be performed by a central laboratory |
| Other study specific tests | 
 • FPG, HbA1c, fasting C-peptide, SMPG |

| Laboratory tests | Parameters |

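### The SAP plans no summary of calcitonin, although the protocol collects it at five on-treatment visits and names thyroid medullary cancer as a risk

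*SAP*

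**What the plan says.** **Collection.** The Schedule of Activities (protocol 1.3) has a central-laboratory row for "Amylase, lipase, calcitonin", marked at screening, at Weeks 4, 8, 12, 18 and 24, and at early discontinuation. Protocol Table 8 (Appendix 2) includes calcitonin among the required chemistry tests: "Total protein Amylase Lipase Calcitonin".

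**Risk.** Protocol Table 1 (2.3.1) names "Thyroid medullary cell cancer" as a potential risk. The mitigation it gives is "C-cell hormone calcitonin is measured at screening and patients with calcitonin ≥20 pg/mL (5.9 pmol/L) will be excluded from participation in the study". The same threshold is an exclusion criterion (E 11).

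**Analysis in the protocol.** Section 9.3.5.3 promises by-visit descriptive statistics for laboratory variables and states: "The central laboratory measurements for safety parameters will be analyzed". Safety laboratory values are part of the secondary safety endpoints.

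**Analysis in the SAP.** Section 3.6.3.1 opens its list with "The following laboratory variables, vital signs and electrocardiogram (ECG) variables will be analyzed" and then enumerates the variables. The relevant line is "Metabolism: glucose, total protein, lipase, amylase". Appendix 6 has criteria for lipase and amylase and none for calcitonin.

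**The concern.** Three analytes share one row of the Schedule. Two of them reach the SAP list and the third does not. The missing one is the marker the protocol pairs with a named risk of clinical significance.

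A programmer following the SAP would produce no calcitonin table: no distribution by visit, no change from baseline, no worst value and no count by arm. A general statement that safety laboratory values raised no concern would then not rest on any planned look at calcitonin values. Any summary added later would be defined after the data had been seen, in an open-label trial where one arm contains a GLP-1 receptor agonist.

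**Working it through.** The plan states no figure on this point that could be reproduced. The check sets the documents side by side and adds one count.

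**1. Is calcitonin the only gap in the chemistry list?** Table 8 names 15 chemistry tests, counting total and direct bilirubin separately: blood urea nitrogen, creatinine, glucose, potassium, sodium, calcium, AST, ALT, alkaline phosphatase, total bilirubin, direct bilirubin, total protein, amylase, lipase and calcitonin. SAP 3.6.3.1 carries 14 of these (15 - 14 = 1 missing). The missing one is calcitonin. All Table 8 hematology tests are carried over.

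**2. Is the SAP list open or closed?** The lead-in says the variables that follow will be analysed. It does not present them as examples. The descriptive-statistics sentence in 3.6.3.1 and the sentence on the incidence of potentially clinically significant abnormalities (PCSAs) are each limited to the variables *above*. Calcitonin is not among them.

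**3. Does another SAP provision bring it in?**
- Appendix 6 has no calcitonin row.
- The operative PCSA list is the sponsor's list in force at database lock. Its content is not in the documents.
- Parameters without a PCSA criterion are to be compared with the normal range where applicable. That sentence does not itself contain the word *above*, but the incidence summary it feeds does.
- The adverse events of special interest in SAP Table 6 are pregnancy, symptomatic overdose and ALT above 3 times the upper limit of normal. Calcitonin is not one of them.

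**4. Was the omission declared?** The SAP states that there are no major changes from the protocol's analyses. Its version history logs one item, the estimand for total insulin dose. Nothing records a decision to leave calcitonin out. Phosphorus, in footnote k of the Schedule, is also absent from the SAP list, which fits an oversight better than a decision.

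**5. How much data is involved?**
- Inputs: 580 participants, 290 per arm, and 10% dropout (SAP section 4); 5 scheduled on-treatment samples each (Schedule of Activities).
- All samples taken: 580 x 5 = 2,900, or 290 x 5 = 1,450 per arm.
- If the 10% who drop out gave no on-treatment sample: 580 x 0.9 = 522, and 522 x 5 = 2,610.
- Scheduled results without a planned summary: about 2,610 to 2,900, plus early-discontinuation samples.

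**6. What would the baseline be?** No calcitonin is drawn at the randomization visit. Under the SAP's rule (last value before first injection) the screening value would normally serve as baseline, so change from baseline can be computed without new data.

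**The case against.** The strongest reply is that calcitonin works here as a screening test. Table 1 says "C-cell hormone calcitonin is measured at screening" and goes no further, whereas for the pancreas the same table says enzymes are monitored during the study. On-study calcitonin therefore has no stated purpose, it is not an event of special interest, and the safety analyses are descriptive with no testing planned (SAP 3.6).

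The part about Table 1 stands: the link between the on-treatment samples and the thyroid risk is an inference. It does not remove the gap. The protocol orders those samples, lists the test as required, and says central safety measurements will be analysed. Either they are summarised or the SAP should say why not.

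A reader might go further and infer that the study report would hold no calcitonin result, or that a participant with a raised value would appear in no table. The documents do not support that. Protocol 8.2.4 has investigators record clinically significant laboratory changes as adverse events, and the SAP tabulates all treatment-emergent events. Protocol 9.3.5.3 still covers central safety measurements in general terms, and the PCSA list at database lock may differ from Appendix 6. The adverse event route is narrower than a laboratory table, however. It depends on individual judgement in an open-label trial and gives no distribution and no uniform count by arm.

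Nor is this an outright contradiction of 9.3.5.3, which is generic and does not name calcitonin. It is incomplete carry-over from protocol to SAP. The number of participants who might reach 20 pg/mL cannot be estimated, because the documents give no rate.

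**Conclusion.** The point holds as an omission that should be corrected. As written, the SAP plans no summary of calcitonin values. Only rises judged clinically significant would be reported, as adverse events. The size is one analyte out of 15 required chemistry tests, and roughly 2,610 to 2,900 scheduled on-treatment results. The primary and key secondary analyses are untouched.

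This rests on two readings. The first is that the SAP list is exhaustive, which its lead-in and the two references to variables *above* support. The second is that the normal-range fallback applies only to listed variables, which is plausible but not explicit. If the fallback were read more broadly, an abnormality count might be produced, but the by-visit and worst-value summaries would still be missing.

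The 20 pg/mL threshold is an entry criterion. The documents do not make it an on-treatment abnormality criterion.

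**What to change.** 1. Add calcitonin to the list in SAP 3.6.3.1, so that it receives by-visit, last and worst on-treatment values with change from baseline.
2. Report the number and percentage of participants by arm with any on-treatment value above the normal range. This is the SAP's own default where no PCSA criterion exists.
3. Optionally, add a count by arm and a listing of on-treatment values of 20 pg/mL (5.9 pmol/L) or more. Label it a descriptive reporting category taken from the entry threshold, with no implication for participant management.
4. If the sponsor prefers not to analyse on-treatment calcitonin, state that and the reason in the SAP.

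The cost is one line in the SAP and one or two tables from data already collected, with no protocol change and no extra sampling. Phosphorus can be checked at the same time.

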3.6.3.2 Analysis of hypoglycemia

Hypoglycemia events will be identified from e-CRF “Hypoglycemic Event Information”. Analyses of hypoglycemia will be performed on events occurring during the on-treatment period and post-treatment period, including any hypoglycemia, level 1 hypoglycemia, level 2 hypoglycemia, level 3 hypoglycemia, hypoglycemia occurred on daytime, hypoglycemia occurred nocturnally, defined as:

- Any hypoglycemia event meeting ADA definition Level 1, Level 2, or Level 3.
- Level 1 hypoglycemia: a measurable glucose concentration <70 mg/dL (3.9 mmol/L) but ≥ 54 mg/dL (3.0 mmol/L).
- Level 2 hypoglycemia: a blood glucose concentration <54 mg/dL (3.0 mmol/L).
- Level 3 hypoglycemia: a severe event characterized by altered mental and/or physical functioning that requires assistance from another person for recovery, corresponding to e-CRF “Required Assistance Because Subject Was Not Capable of Helping Self” ticked for “Assistance Required?”.
- Hypoglycemia occurred on daytime: on e-CRF page “Hypoglycemic Events” the “Time of Event” is between 6:00 to 23:59 (inclusive). An additional analysis will be performed for events with “Between Waking and Bedtime” ticked for “When did the Hypoglycemic Event occur?”.
- Hypoglycemia occurred nocturnally: on e-CRF page “Hypoglycemic Events” the “Time of Event” is between 0:00 to 5:59 (inclusive). An additional analysis will be performed for events with “Between Bedtime and Waking” ticked for “When did the Hypoglycemic Event occur?”.

The number (n) and incidence rate (%) of participants experiencing at least one specific hypoglycemic event will be summarized by treatment group. Each hypoglycemic endpoint will be analyzed using a logistic regression model adjusting for treatment group, randomization strata of HbA1c and previous OADs and appropriate baseline covariates. The proportion of participants in each treatment group will be provided, as well as the odds ratio between groups with associated 2-sided 95% CI. Level 1 hypoglycemia and Level 2 hypoglycemia during on-treatment period will be analyzed further by symptoms (symptomatic or asymptomatic) with the same methodology.

The hypoglycemic event rate per participant year will be derived for each type of hypoglycemia and will be summarized by treatment group. A negative binomial model will be fitted in SAS to estimate the event rate. The number of hypoglycemic events is the response variable. The independent variables will be treatment group, randomization strata of HbA1c and previous OADs used as fixed effects and appropriate baseline covariates. The logarithm of the duration (in years) of open-label randomized treatment period as an offset variable to account for unequal follow-up time due to early withdrawal, rescue medication, etc. The ratio of hypoglycemic events rate and its 2-sided 95% CI will be presented. The estimated mean hypoglycemic events in two groups along with their 95% CIs are presented from this model.

The pattern of symptomatic hypoglycemia occurrence over time will also be assessed, if appropriate. The number (%) of participants with at least 1 symptomatic hypoglycemia with blood glucose concentration <70 mg/dL (3.9 mmol/L) during the on-treatment period will be assessed over time, using weekly time intervals up to 24 weeks, ie, [0-1] week, (1-2] weeks, (2-3] weeks, (3-4] weeks, etc. In each time interval, the numerator in the calculation of percentages will be the number of participants with at least 1 event occurring in this time interval. Two types of analyses will be performed: (1) only the first event will be counted for each participant and all recurrent events will not be included, and the denominator will be the number of participants at risk at the beginning of the time interval who did not experience a first event in the preceding intervals; and (2) the recurrent events in subsequent intervals will be counted once for each participant in the numerator of the corresponding interval, and the denominator will be the number of participants at risk at the beginning of the time interval.

A Kaplan-Meier curve will also be provided for the time to first symptomatic hypoglycemia with blood glucose concentration <70 mg/dL (3.9 mmol/L) during the on-treatment period.

The number (%) of participants with at least 1 symptomatic hypoglycemia with blood glucose concentration <70 mg/dL (3.9 mmol/L) during the on-treatment period, as well as the corresponding number of events, will be summarized as necessary by hour of the day for each treatment group, using the following hour intervals: $\geq 23:00$ to $<06:00$, $\geq 06:00$ to $<10:00$, $\geq 10:00$ to $<14:00$, $\geq 14:00$ to $<18:00$, $\geq 18:00$ to $<23:00$.

3.7 OTHER ANALYSES

3.7.1 Other variables and/or parameters

Not applicable.

3.7.2 Subgroup analyses

Depending on the data availability (categories with fewer than 5 participants may be combined with other categories), subgroup analyses will be performed on the primary endpoint to summarize the treatment effects across subgroups defined by the following baseline or screening factors:

- Age group (<50 , ≥ 50 to <65 , ≥ 65 to <75 , ≥ 75 years).
- Sex (Male, Female).
- Baseline BMI level (<24 , ≥ 24 to <28 , ≥ 28 kg/m²).
- Randomization stratum of screening HbA1c ($<8\%$, $\geq 8\%$).
- Randomization stratum of oral antidiabetic use at screening (Metformin \pm SGLT-2i / Metformin + other OAD).
- Baseline fasting C-peptide level by quartiles.

The same imputed datasets for primary analysis will be used for the subgroup analyses. Treatment-by-subgroup interaction term and the subgroup factor term will be added in the primary model. In the case that the subgroup factor is identical or similar to a randomization stratum factor, the stratum factor will not be kept in the model.

The treatment effects (iGlarLixi versus IDegAsp) for the primary endpoint will be provided, as well as the corresponding 95% CI, for each subgroup, and the interaction p-value, using the same method as applied to the primary analysis of primary estimand. Forest plots will be provided.

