3.1 APPROPRIATENESS OF MEASUREMENTS

The primary efficacy variable is HbA1c values which reflects the glycemic history of the previous 120 days and is thus an index of mean glycemia, documenting glycemic control over the past 2 to

3 months. HbA1c has also been shown to correlate with the development of long-term complications of diabetes, and reduction of HbA1c is known to reduce the risk of long-term microvascular complications. Therefore, HbA1c is considered an appropriate primary endpoint for assessing the effect of a treatment on glycemic control. In addition to the analysis of the change from baseline in HbA1c, the responder analysis allows the clinical relevance of the reduction observed in HbA1c to be demonstrated. The duration of study treatment is considered to be sufficient for achieving stable conditions with IMP after dose titration and for enabling an adequate assessment of time dependent changes in HbA1c and the concomitant risk of hypoglycemia.

The problem of weight gain in T2DM is widely recognized. Consequently, iatrogenic weight gain is not only unwelcome, but represents an important clinical issue that can become a barrier to the successful management of glycemic control. Body weight control is one of the reasons to choose a GLP-1 RA instead of rapid-acting insulin to intensify basal insulin therapy in this overweight or obese type 2 diabetes population. Taking into account the major impact of insulin-related body weight gain, it is appropriate to include body weight change as secondary efficacy endpoint.

Insulins target primarily, although not exclusively, fasting hyperglycemia, therefore, assessment of fasting glucose is relevant in this study. The 7-point SMPG profiles are also considered as a valuable parameter for monitoring the overall glycemic control throughout the day. β -cell function will be assessed by fasting C-peptide at baseline and Week 24. The glycemic biomarker (HbA1c) will be further evaluated based on the baseline fasting C-peptide levels and therefore to provide evidence that iGlarLixi is effective regardless of baseline β -cell function in patients with T2DM suboptimal controlled with OADs. The effect of iGlarLixi in preservation of β -cell function could also be evaluated via the change in fasting C-peptide from baseline to Week 24 (16).

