4 SAMPLE SIZE DETERMINATION

A total sample size of 580 participants (randomization ratio 1:1, ie, 290 per intervention group) will be determined to demonstrate noninferiority of iGlarLixi versus IDegAsp in HbA1c reduction at Week 24 with 90% power and 2-sided significance level of 0.05 based on the following assumptions on the primary endpoint:

- True mean difference of zero between iGlarLixi and IDegAsp
- Common standard deviation of 1.05%
- Non-inferiority margin on the mean difference of 0.3%
- Dropout rate of 10%

Calculations were made based on two sample t-test using SAS® (Version 9.4).

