5.3 APPENDIX 3 DEMOGRAPHICS AND BASELINE CHARACTERISTICS, PRIOR OR CONCOMITANT MEDICATIONS

Demographics, baseline characteristics, medical surgical history

The following demographics and baseline characteristics, medical and surgical history and diabetes history will be summarized using descriptive statistics in the randomized population.

Demographic and baseline characteristics

- age in years as quantitative variable and in categories (<50, \geq 50 to <65, \geq 65 to <75, \geq 75)
- gender (Male, Female)
- race (Asian)
- baseline body mass index (BMI) in kg/m² as quantitative variable and in categories (<24, \geq 24 to 28, \geq 28)
- randomization stratum of screening HbA1c (<8%, \geq 8%)
- randomization stratum of oral antidiabetic use at screening (Metformin \pm SGLT-2i, Metformin + other OAD)

Baseline efficacy characteristics

- HbA1c % as quantitative variable
- body weight in kg as quantitative variable
- fasting plasma glucose in mmol/L as quantitative variable

- 7-point SMPG in mmol/L as quantitative variable in daily average
- fasting C-peptide level in nmol/L as quantitative variable and by quartiles

Baseline safety will be presented along with the safety summaries.

General medical/surgical history will be collected. Medical and surgical history will be coded to a LLT, PT, HLT, HLGT, and associated primary SOC using the MedDRA version currently in effect at Sanofi at the time of database lock.

Diabetes history

- Duration of type 2 diabetes in years derived as: (Date of informed consent – Date of diagnosis of diabetes + 1)/365.25
- Age at onset of diabetes in years derived as: Year of diagnosis of diabetes – Year of birth
- Duration of prior metformin treatment in years derived as: (Date of informed consent - Date of first intake of metformin + 1)/365.25
- Baseline daily dose metformin in mg as quantitative variable and in categories (<1000, \geq 1000 to <1500, \geq 1500 to <2500, \geq 2500)
- Prior use of SGLT-2i (Yes, No)
- Duration of prior SGLT-2i treatment in years derived as: (Date of informed consent – Date of first intake of SGLT-2i + 1)/365.25
- Prior use of OADs other than metformin or SGLT-2i (Yes, No)
- Duration of prior OADs other than metformin or SGLT-2i in years derived as: (Date of informed consent - Date of first intake of OAD + 1)/365.25
- Gestational diabetes
- Diabetic retinopathy
- Diabetic neuropathy
- Diabetic nephropathy

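### Baseline C-peptide is examined as an effect modifier only through a quartile interaction, which is inefficient for a graded effect; a 1-df continuous interaction should be added beside it.

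*SAP*

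**What the plan says.** SAP 3.7.2 includes "Baseline fasting C-peptide level by quartiles" among the subgroup factors for the primary endpoint, as Protocol 9.3.2 does. On the model, the SAP says: "Treatment-by-subgroup interaction term and the subgroup factor term will be added in the primary model". Its outputs are the treatment difference with a 95% CI "for each subgroup, and the interaction p-value, using the same method as applied to the primary analysis of primary estimand", plus forest plots. The degrees of freedom are not stated, but four quartiles by two arms imply 3.

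C-peptide as a continuous variable appears only in the baseline summary of SAP 5.3: "fasting C-peptide level in nmol/L as quantitative variable and by quartiles".

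Protocol 3.1 gives the analysis a purpose. HbA1c is to be examined by baseline C-peptide, "therefore to provide evidence that iGlarLixi is effective regardless of baseline β -cell function". Neither document gives an interaction effect size, an interaction power, or a rule for reading a non-significant interaction.

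**The concern.** C-peptide is a continuous physiological measure, and a graded relation with treatment effect is a natural alternative to no relation. An unordered quartile interaction ignores the order of the quartiles and the variation within them, and it spends 3 degrees of freedom where a gradient needs one.

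This matters more here than for a routine demographic subgroup, because Protocol 3.1 hopes for an effect that does not depend on the baseline level. Low sensitivity makes it easier to report a consistent effect when a real gradient exists.

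**Working it through.** **Inputs.** SAP section 4 (same in Protocol 9.1): "A total sample size of 580 participants (randomization ratio 1:1, ie, 290 per intervention group"), "with 90% power and 2-sided significance level of 0.05", SD 1.05%, margin 0.3%, true difference 0, dropout 10%. Assumptions not in the documents: effect modification linear in C-peptide, C-peptide roughly normal (for example after a log transform), and the reference power of the 1-df test.

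**The plan's own figure.** n per arm = 2 × (1.960 + 1.282)² × 1.05² / 0.3² = 258 after rounding up (259 with the t-distribution). 258 / 0.9 = 287 per arm, against the stated 290. The sample size reproduces closely, but it concerns the primary comparison and not any interaction.

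**Variance kept by quartiles.** The quartile means of a standard normal variable are ±1.271 and ±0.325. The share of variance kept is (1.271² + 0.325²) / 2 = 0.861.

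**Power of the quartile test.** At two-sided 5%, a 1-df test with 80% power has noncentrality 7.849. With 3 df and no other loss, power would be 64%. Including the loss within quartiles, 7.849 × 0.8606 = 6.755, and chi-square power on 3 df is 57.3% (57.1% by the F distribution with N = 522 or 580). Other reference values:

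| 1-df power | Quartile test, 3 df |
|---|---|
| 50% | 30% |
| 70% | 47% |
| 80% | 57% |
| 90% | 71% |
| 95% | 81% |

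**Gradient needed for the 80% case.** Evaluable N = 580 × 0.9 = 522. The SE of the interaction slope per SD of C-peptide is 2 × 1.05 / √522 = 0.0919. The detectable slope is 2.80 × 0.0919 = 0.257 HbA1c points per SD. Lowest and highest quartile means are 2 × 1.271 = 2.542 SD apart, so the contrast is 0.257 × 2.542 = 0.65 points. With N = 580 it is 0.62.

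**Power by size of contrast (N = 522, SD 1.05%).**

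| Lowest-to-highest-quartile contrast | 1-df continuous | 3-df quartile |
|---|---|---|
| 0.25 | 19% | 12% |
| 0.38 | 37% | 22% |
| 0.51 | 59% | 36% |
| 0.76 | 90% | 72% |

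**Other shapes.**
- Lognormal C-peptide (log-SD 0.3 to 0.6) with an effect linear on the raw scale: 80% becomes 55% to 48%.
- Only the lowest or only the highest quartile differs: the squared correlation of that indicator with a normal covariate is (0.25 × 1.271)² / (0.25 × 0.75) = 0.539. When the 3-df test has 80% power (noncentrality about 10.9), the 1-df test has noncentrality 10.9 × 0.539 = 5.87, or 68% power. Here the quartile test is better.

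**Precision.** The 95% CI half-width for one quartile's treatment difference is 1.96 × 1.05 × √(4 / 130.5) = 0.36 points (0.34 with N = 580), wider than the 0.3 margin. Under a linear model it is 1.96 × 0.0919 = 0.18 at mean C-peptide, and 0.18 × √(1 + 1.271²) = 0.29 at the mean of an extreme quartile.

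**The case against.** The strongest reply is that this is a choice between two defensible codings.

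- Quartiles assume no shape and no raw or log scale, and they win when the effect is confined to one extreme quartile. Nothing in the documents says modification must be graded. This stands, and it is why the quartile test should not be replaced.
- The 80% is a chosen reference. It needs a contrast more than twice the non-inferiority margin. At 0.38 points or less the continuous test would also usually be non-significant, so a change of coding alone does not prevent a null result from being over-read. This stands too.
- The interaction p-value is not the only output. Quartile estimates, CIs and forest plots are planned; an ordered pattern could be seen there, and the wide intervals would show the imprecision. The subgroups also sit outside the multiplicity procedure and carry no confirmatory claim.
- A reader might infer from Protocol 3.1 that the plan will take a non-significant interaction as proof of a uniform effect. The documents contain no such rule. The wording can equally mean effective at each C-peptide level, which the quartile estimates address.
- The 522 is a working figure. The subgroup models use the imputed datasets for all randomized participants. The effect on the results is small.

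What remains is that the only planned test is poorly matched to a graded effect, in an analysis with a stated purpose, and Protocol 9.3.2 leaves room for further subgroup analyses in the SAP.

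**Conclusion.** The point holds as a low-cost improvement and is not an error in the plan. For a linear gradient over a roughly normal C-peptide, the quartile interaction turns 70%, 80% or 90% power into about 47%, 57% or 71%. These figures are conditional on that shape and on the reference power. The 80% case further rests on 522 evaluable participants, SD 1.05% and a contrast of about 0.65 HbA1c points.

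It would be wrong to conclude that this trial's C-peptide interaction test has 57% power. No interaction power is stated, and the true value depends on an unknown gradient. It would also be wrong to conclude that quartiles are inferior in general, since the order reverses for an effect in one extreme quartile. The primary and key secondary analyses are unaffected.

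**What to change.** In SAP 3.7.2:

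1. Keep the quartile estimates, interaction p-value and forest plot.
2. Add a prespecified model: the primary ANCOVA plus log(baseline C-peptide) and its product with treatment (1 df), fitted to the same imputed datasets and combined by Rubin's rule.
3. Plot the estimated treatment difference with its 95% CI across the observed C-peptide range.
4. State that a non-significant interaction, under either coding, does not by itself show that the effect holds regardless of β-cell function.

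The cost is one extra exploratory model, one p-value and one figure. The added test assumes a linear gradient on the log scale, which the retained quartile analysis checks. Data collection, imputation and the confirmatory tests do not change.
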